Preprocessing: Post-acquisition preprocessing and statistical analysis of all of the neuroimaging data will be performed using FEAT (FMRI Expert Analysis Tool) Version 5.98, part of FSL (FMRIB's Software Library, www.fmrib.ox.ac.uk/fsl). Functional magnetic resonance imaging (fMRI) blood oxygen level dependent (BOLD) imaging data will be acquired using a standard multi-slice gradient echo planar imaging sequence (TR=2200 ms, TE=35 ms, 64 x 64 matrix, 3 mm isotropic voxels, 271 volumes). Data will be preprocessed using scripting tools from FMRI Expert Analysis Tool (FEAT) Version 5.98, part of FMRIB's Software Library (FSL; www.fmrib.ox.ac.uk/fsl). First non-brain signal will be removed using FSL's BET brain extraction. Scans will be corrected for motion using FSL's linear registration and scans will be spatially smoothed using a Gaussian kernel of 8 mm FWHM. Since head motion can impact functional connectivity analyses, participants with head motion exceeding 0.2 mm will be excluded from the analyses (Power et al., 2012). The "fsl_motion_correction" scripting tool will be used to identify and scrub motion artifacts from each participant's data (Power et al., 2013). Scans will be spatially co-registered with a standardized anatomical template (Montreal Neurological Institute) using a 12 parameter affine transformation (Rorden et al., 2000). **Analysis:** Functional connectivity will be measured using a PPI based approach (Friston et al., 1997). A customized square wave form representing the task (1 = stress condition and -1 = control condition) and the duration of each condition will be convolved with a double-gamma hemodynamic response function. A mask of the seed region will be made using a 12-mm diameter sphere located in the center of the left amygdala using the MNI coordinates (x, y, z = -22, 0, -22). The transformation parameters described above will also be applied to the mask. For each participant and each run of the MIST, the mean corrected and high pass filtered time series of the BOLD signal in the left amygdala will be extracted and used in a single subject whole brain PPI analysis. The PPI model will include (1) the task vector; (2) the time series of the BOLD signal in the left amygdala; (3) a term representing the positive task x seed interaction; and (4) a term representing the negative task x seed interaction. The first level analysis will generate contrast images of the parameter estimates for each of the four regressors. Since the hypotheses associated with Specific Aim 1 explore increases in amygdala - prefrontal cortical connectivity in response to social stress, the group analysis will focus on the positive interaction term. The contrast images of the parameter estimates of the positive interaction term will be entered into a 2nd-level random effects analysis. Unpaired t-tests will be used to test for the following group differences (Hypothesis 1A: CD-PBO vs. HC-PBO) and (Hypothesis 1B: CD-OT vs. CD-PBO). Analyses will be conducted using FMRIBs Local Analysis of Mixed Effects (FLAME 1). Additional analyses comparing (HC-OT vs. CD-OT) will be conducted using an unpaired t-test and applying the appropriate corrections for multiple tests. We will also conduct an exploratory gender analysis between the CD and HC women in the four groups (Domes, Heinrichs, Glascher, et al., 2007; Domes et al., 2010; Potenza et al., 2012). We anticipate that 15-20% of the subjects in each group will be female (n=6/8 per group). We

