Data Analysis: Following preprocessing (described above), within-task data from individual participants will be analyzed with a fixed-effects general linear model (GLM), with each emotion (described below) modeled as a box-car function convolved with a double-gamma hemodynamic response function. The response period at the end of each block will also be modeled as a separate variable to remove effects of explicit decision making and response selection. The GLM procedure is repeated for each voxel with six movement parameters (3 rotation values in radian and 3 translation values in millimeter) included as covariates to control for the influence of head motion on the data. Following first-level analysis, subject-specific contrasts will be entered into second-level, random-effects analyses. Since the hypotheses associated with Specific Aim 2 explore amygdala activity, we will use a region of interest approach (ROI). The BOLD signal from the left amygdala will be extracted using an anatomical mask generated by a 12-mm diameter sphere located in the center of the left amygdala using the MNI coordinates (x, y, z = -22, 0, -22). The percent signal change between the fearful and neutral conditions (contrast of interest) will be calculated for each participant. Separate random-effects one-way analysis of variance tests (ANOVA) will be used to test for the following group differences (Hypothesis 2A: CD-PBO vs. HC-PBO) and (Hypothesis 2B: CD-PBO vs. CD-OT). Since human neuroimaging studies have found that other brain regions play a role in implicit emotional processing, including the right amygdala and insula (Davidson et al., 1999; Shi et al., 2013), secondary analyses will also include these regions. In addition, OT may impact amygdala responding to happy faces (Domes, Heinrichs, Glascher, et al., 2007), therefore group differences in amygdala responding in the happy-neutral contrast may be explored in future analyses. For multiple comparisons that are not part of the hypothesis a priori, the Bonferroni correction will be used. In addition, contrasts of other pertinent baseline characteristics will be performed between groups. If the groups differ significantly on any of these baseline characteristics, the corresponding variables will be used as covariates in the above analyses. The statistical analyses will be conducted using SAS 9.3 software (SAS Institute Inc., Cary, NC, USA).

Power and Sample Size

Specific Aim 1

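### The Aim 1 connectivity model lists no movement parameters, although the Aim 2 model adds six after the same motion preprocessing; residual motion could mask or reverse the predicted 1A and 1B differences

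*Combined protocol and SAP*

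**What the plan says.** The Aim 1 model is set out in section C3f, Statistical Methods, under Hypotheses 1A and 1B (Analysis). Its first two terms are given as "The PPI model will include (1) the task vector; (2) the time series of the BOLD signal in the left amygdala", and the other two as "3) a term representing the positive task x seed interaction; and (4) a term representing the negative task x seed interaction". The text then says "The first level analysis will generate contrast images of the parameter estimates for each of the four regressors". The group comparisons use the positive interaction term.

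Motion is handled earlier, in the Preprocessing paragraph of the same section, by three steps:

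- realignment: "Scans will be corrected for motion using" FSL's linear registration;
- exclusion: "Since head motion can impact functional connectivity analyses, participants with head motion exceeding 0.2 mm will be excluded from the analyses";
- scrubbing: a named "scripting tool will be used to identify and scrub motion artifacts from each" participant's data.

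The Aim 2 Data Analysis paragraph says that its model follows the preprocessing already described, so it inherits all three steps. It then has "six movement parameters (3 rotation values in radian and 3 translation values in millimeter) included as covariates to control for the influence of head motion".

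Section 5.1 (Summary of the Protocol) names amygdala–prefrontal connectivity during the MIST stress condition as a primary outcome.

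**The concern.** A PPI asks whether the relation between seed and target differs between stress and control blocks. Head motion can add a common signal to both regions. If that signal is stronger in stress blocks, part of it appears as a stress-minus-control change in coupling, which is the quantity tested. An activation contrast in one region, as in Aim 2, does not depend on a shared seed-target signal in this way. Yet Aim 2 is the analysis with the extra motion covariates.

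Motion that depends on condition and group is plausible here, though not documented. Section C2a reports significantly greater MIST anxiety in cocaine-dependent pilot participants than in controls, and Hypothesis 1C predicts less anxiety under oxytocin. If anxiety affects movement, the compared groups could differ in stress-block motion. Randomisation does not protect 1B, because motion in the scanner arises after treatment.

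**Working it through.** **Step 1. Reproduce the plan's count.** The inputs are the term lists in section C3f.

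| | Aim 1 PPI | Aim 2 GLM |
|---|---|---|
| Realignment, 0.2 mm exclusion, scrubbing | yes | yes (same preprocessing) |
| Listed model terms | task, seed, positive interaction, negative interaction | emotion conditions, response period |
| Movement parameters | 0 | 6 |

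The Aim 1 terms number 1 + 1 + 1 + 1 = 4, which matches the plan's own figure of four. The preprocessing is common to both models, so it cannot account for the difference of six covariates.

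**Step 2. Direction of the possible bias.** This is a simplified argument that ignores the haemodynamic response and the rest blocks. Let the seed be s = s0 + a·m and the target y = y0 + b·m, where m is residual motion with variance σ² in stress blocks and none in control blocks. Let v be the variance of s0, let β be the true slope of y0 on s0, and let m be independent of both.

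- Slope in control blocks: β.
- Slope in stress blocks: (βv + abσ²) / (v + a²σ²).
- Difference, stress minus control: aσ²(b − βa) / (v + a²σ²).

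The added covariance, abσ², is positive when a and b have the same sign. The slope rises when, in addition, b/a exceeds β, as it does when true coupling is weak. Under those conditions, apparent stress-related coupling rises in whichever group moves more under stress.

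Applied to the hypotheses:

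- 1A predicts HC-PBO > CD-PBO. More stress-block motion in CD-PBO raises the right-hand side, so the predicted difference shrinks or reverses.
- 1B predicts CD-OT > CD-PBO. If oxytocin calms participants and they move less, CD-PBO is again the inflated group and the predicted difference shrinks or reverses.

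**Step 3. Size.** The bias depends on a, b and σ² after exclusion and scrubbing, and on how σ² differs by block and group. The documents give none of these, so no error rate or power loss can be calculated from them.

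**Step 4. Cost of adding six parameters.** Nominal residual degrees of freedom per run = volumes − regressors − 1 (intercept), counting each listed regressor as one column and ignoring autocorrelation, filtering and scrubbed volumes. The regressor count goes from 4 to 4 + 6 = 10. The number of volumes per run is uncertain, because the stated acquisition figures disagree: MRI Data Acquisition gives TR 2500 ms, Preprocessing gives TR 2200 ms and 271 volumes, and the MIST section gives six-minute runs (360 s). At 2.2 s, 271 volumes would last 271 × 2.2 = 596 s, or about 9.9 minutes. All three possibilities are shown.

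| Basis | Volumes | 4 regressors | 10 regressors | Loss |
|---|---|---|---|---|
| Stated volume count | 271 | 266 | 260 | 6/266 = 2.3% |
| 360 s / 2.2 s | 163 | 158 | 152 | 6/158 = 3.8% |
| 360 s / 2.5 s | 144 | 139 | 133 | 6/139 = 4.3% |

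**The case against.** The strongest reply is that motion is already controlled in Aim 1, by three separate steps. That is correct, and a reader who inferred from the four-term list that Aim 1 ignores motion would be wrong. But the same steps precede Aim 2, where six covariates were still thought worth adding, and the plan gives no reason for treating the connectivity model differently.

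A second reply is that the sentence about four regressors describes contrast images, which nobody needs for nuisance terms, so nuisance terms might be present but unlisted. The plan also does not say whether scrubbing deletes volumes or enters confound regressors; if the latter, some motion terms are already in the model. Both points are fair, and the omission may be one of reporting. However, the preceding list of what the model includes names no nuisance terms. Scrubbing regressors would deal only with flagged volumes, leaving motion below the threshold unmodelled.

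A third reply concerns the harm. A reader might infer that the omission produces false support for 1A and 1B, or inflates the error rate by some known amount. The documents support neither. Under the most plausible scenario the bias runs against both hypotheses, and no figure can be attached to it without assuming how much motion survives preprocessing and how it differs by block and group. The planned inference is also a whole-brain, cluster-corrected analysis, so a calculation for a single target would not carry over directly. This reply stands.

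**Conclusion.** The inconsistency is real. As written, the Aim 1 PPI model has no movement parameters, while the Aim 2 model has six after the same preprocessing, and the plan itself names motion as a threat to connectivity analyses. The consequence is a possible bias of unknown size on a primary outcome.

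The stated direction, towards masking or reversing the predicted differences, rests on three assumptions: CD-PBO participants move more in stress blocks than the comparison group; some of that motion survives exclusion and scrubbing; and it enters seed and target with the same sign, by enough to raise the slope. None can be checked from the documents. If the sign or the group pattern differed, so would the direction.

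This is a worthwhile, inexpensive improvement. It does not show that the connectivity analysis is invalid.

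**What to change.** State in the Aim 1 analysis paragraph that the six realignment parameters enter every run-level PPI model as nuisance regressors, as in Aim 2, and that scrubbed volumes are carried as confound regressors. If this was always intended, one sentence saying so settles the matter.

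Realignment already produces the parameters, so no new data are needed. The six parameters cost about 2% to 4% of nominal residual degrees of freedom per run. Scrubbing regressors use further degrees of freedom according to how many volumes are flagged, which the documents do not indicate. If movement tracks the stress blocks, the parameters may also remove some genuine task-related signal.

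A reader might expect the change to remove the problem altogether. It will not: realignment parameters are an imperfect proxy for the motion artefact, so the bias is reduced, not eliminated.

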NCT#02682784

Title: Neural substrates of emotion: Impact of cocaine dependence

Document Date: 06/18/2020

NEURAL SUBSTRATES OF EMOTION: IMPACT OF COCAINE DEPENDENCE

SPECIFIC AIMS

Over one million individuals in the United States meet criteria for cocaine use disorders. Relapse rates are highest among cocaine-dependent (CD) populations. Social stress is a significant risk factor for relapse. Data from human neuroimaging studies suggest that “top-down” prefrontal cortical inhibition of amygdala activity controls emotional responses to social stimuli. A growing literature suggests that hypoactivity in the medial prefrontal cortex coupled with increases in amygdala activity underscore the vulnerability of CD individuals to relapse. Neuroimaging studies of corticolimbic network activity (functional connectivity) have been conducted in CD subjects at rest. Compared with healthy controls, CD subjects exhibited lower corticolimbic connectivity and the degree of corticolimbic uncoupling was associated with time to relapse. Studies measuring corticolimbic connectivity during exposure to a social stress task in CD subjects could provide critical insight into the neurobiologic mechanisms that underscore the sensitivity of CD individuals to social stress. Moreover interventions that improve corticolimbic connectivity in CD subjects may be effective therapeutic strategies for preventing relapse in CD populations. Oxytocin (OT) is an anxiolytic neuropeptide that attenuates amygdala responses to aversive social cues. In order to better understand the neurobiologic mechanisms that control emotion-related behavior in CD populations, we propose a double-blind placebo (PBO) controlled study using blood oxygen level dependent (BOLD) functional magnetic resonance imaging (fMRI) to measure (1) corticolimbic functional connectivity during the Montreal Imaging Stress Task (MIST) and (2) amygdala activity in response to an implicit facial affect recognition paradigm in groups of CD individuals (CD n=80) and healthy non-dependent controls (HC, n=80). Prior to the scanning session, participants will receive either intranasal OT (24 IU) or PBO spray (n=40 per treatment group). The order of the tasks will be counterbalanced.

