Figure 1. Schematic overview of Specific Aim 1. Corticolimbic functional connectivity during social stress in (A) healthy controls treated with placebo (PBO) (B) cocaine-dependent individuals treated with PBO (C) healthy controls treated with oxytocin (OT) and (D) cocaine-dependent individuals treated with OT. Lines represent the magnitude of functional connectivity between the amygdala and orbital frontal cortex (OFC) and anterior cingulate cortex (ACC).

Hypothesis 1A: A > B

Hypothesis 1B: B < D

amygdala connectivity with the salience network, a finding that has been associated with OTs effects on empathy and trust (Riem et al., 2011; Riem et al., 2012; Seeley et al., 2007; Striepens et al., 2012). Interestingly, intranasal OT can attenuate functional connectivity between the amygdala and brain regions responsible for regulating autonomic and endocrine manifestations of fear and anxiety (Kirsch et al., 2005). **These studies suggest that intranasal OT enhances amygdala connectivity with prefrontal cortical brain regions (Figure 1C). In the proposed study, we will explore the effect of OT on functional connectivity between corticolimbic regions and its relationship to anxiety and craving in CD individuals and controls.**

Evidence Linking Cocaine Dependence with a Loss of Bottom-Up Control: Role of the Amygdala

The ability to recognize emotional cues from faces is a necessary component of social interactions (Blair, 2003). To date, the impact of cocaine use on facial affect processing remains unclear. For example, clinical studies of CD subjects found no difference between CD and healthy controls in the ability to recognize the emotional expressions of faces (Fox et al., 2011; Hulka et al., 2013). Another study found that compared with healthy controls, recreational cocaine users exhibited deficits in the ability to accurately recognize faces depicting

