
acknowledge that we may be underpowered to conduct these tests. Since there may be important group differences in regional brain activity during the MIST, a secondary whole brain analysis will be conducted using the contrast of interest (stress-control). Analyses will be conducted using FMRIBs Local Analysis of Mixed Effects (FLAME 1). All group level results will be thresholded at $Z>2.3$ using a corrected cluster threshold of $p=0.05$.

Hypothesis 1C: The CD-OT group will report lower subjective anxiety and craving than the CD-PBO group.

Analysis: A linear mixed effects model containing all serially measured time points will be used to assess the effects of OT versus placebo on each dependent variable. Restricted maximum likelihood (REML; Patterson and Thompson, 1971) methods will be used to estimate the fixed effects and variance components, and baseline values will be used as covariates in the regression models. The dependent variables anxiety and craving will be modeled separately. Within each family of dependent measures, the Type I error rate will be controlled using a post-hoc Bonferroni correction. The statistical analyses will be conducted using SAS 9.3 software (SAS Institute Inc., Cary, NC, USA).

Specific Aim 2: Use an implicit facial affect recognition paradigm to determine the impact of cocaine dependence and oxytocin on amygdala activity in response to fearful faces.

Hypothesis 2A: The CD-PBO group will exhibit greater amygdala activity in response to fearful faces than HC-PBO group.

Hypothesis 2B: Compared with the CD-PBO group, participants in the CD-OT group will exhibit lower amygdala activity in response to fearful faces.

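### No named imaging test estimates oxytocin's effect in controls or its difference by diagnosis, and Hypothesis 1C does not say whether controls are in its model

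*Combined protocol and SAP*

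**What the plan says.** - **Design (Specific Aims).** There are 80 CD and 80 HC participants, and within each diagnosis "participants will receive either intranasal OT (24 IU) or PBO spray (n=40 per treatment group"). That makes four cells of 40.
- **Intent (A. Significance, Oxytocin Alters Corticolimbic Connectivity).** The study will "explore the effect of OT on functional connectivity between corticolimbic regions and its relationship to anxiety and craving in CD individuals and controls". Figure 1 has a panel for oxytocin-treated controls, but the hypotheses listed with it compare only HC-PBO with CD-PBO and CD-PBO with CD-OT.
- **Aim 1 connectivity (C3f. Statistical Methods).** Unpaired t-tests are named for "Hypothesis 1A: CD-PBO vs. HC-PBO) and (Hypothesis 1B: CD-OT vs. CD-PBO". Then: "Additional analyses comparing (HC-OT vs. CD-OT) will be conducted using an unpaired t-test", with correction for multiple tests. There is also an "exploratory gender analysis between the CD and HC women in the four groups", with 6 to 8 women per group, no contrast stated and low power conceded. A secondary whole-brain stress-minus-control analysis does not name its groups.
- **Aim 2 amygdala response (C3f).** "Separate random-effects one-way analysis of variance tests (ANOVA) will be used to test for the following group differences": CD-PBO vs HC-PBO (2A) and CD-PBO vs CD-OT (2B). HC-OT is in neither.
- **Hypothesis 1C (C3f; Power and Sample Size).** "The CD-OT group will report lower subjective anxiety and craving than the CD-PBO group". The mixed model compares oxytocin with placebo. It names no population and no diagnosis term. The sample size paragraph counts 35 CD and 35 controls in each treatment arm.

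**The concern.** In a 2x2 design the randomised factor is treatment. The oxytocin effect in controls is HC-OT vs HC-PBO, and whether oxytocin acts differently in cocaine dependence is the interaction. Neither is named. The one full-group imaging contrast that uses HC-OT sets it against CD-OT, which is a non-randomised comparison of diagnoses under drug.

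The protocol's own background leaves specificity open. It cites a resting-state study in which oxytocin raised amygdala-prefrontal connectivity in healthy people. It also cites studies in which oxytocin lowered stress reactivity in people with poor coping but not in healthy controls. A CD-OT vs CD-PBO difference fits either picture.

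There is also a risk of misreading. Suppose 1A shows a group difference on placebo and the additional test shows none on oxytocin. The tempting conclusion is that oxytocin normalises connectivity, but that compares one p-value with another. The quantity needed is the difference between the two contrasts, with its own standard error.

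**Working it through.** **1. Which contrasts are named**

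| Outcome | CD-PBO vs HC-PBO | CD-OT vs CD-PBO | HC-OT vs CD-OT | HC-OT vs HC-PBO | Interaction |
|---|---|---|---|---|---|
| Connectivity | 1A | 1B | additional test | not named | not named |
| Left amygdala response | 2A | 2B | not named | not named | not named |
| Anxiety, craving | not named | 1C | not named | not named; controls may be pooled | not named |

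HC-OT is 40/160 = 25% of the sample.

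**2. What the additional test can and cannot give**

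Interaction = (CD-OT − CD-PBO) − (HC-OT − HC-PBO) = (CD-OT − HC-OT) − (CD-PBO − HC-PBO).

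For connectivity the plan estimates both brackets of the second form (the additional test and 1A) but never their difference. For the amygdala response only the second bracket is planned.

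**3. Which population the 1C sample size assumes**

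Inputs from Power and Sample Size: anxiety difference 1.07, RMSE 2.20 (ratio 0.486, given as 0.49 and then 0.48), 80% power, alpha 0.05, total 140.

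- Two-sided, d = 0.48: n per arm = 2(1.960 + 0.842)²/0.48² = 68.1, so 69, or 138 in total. This reproduces the stated 140.
- One-sided: 54 per arm, 108 in total. This does not.
- Reading the 69 per arm as CD participants only and doubling for controls: 4 × 69 = 276. This does not.

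So of the readings tried, 140 arises only from oxytocin vs placebo with CD and HC pooled, 70 per arm. The CD-only contrast stated in 1C has 40 vs 40:

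- Power = Φ(0.48/√(2/40) − 1.960) = Φ(0.187) = 57%.
- If the outcome is the mean of m ratings with ICC 0.78, the variance factor is (1 + (m − 1) × 0.78)/m, which is 0.835 for m = 4 and 0.824 for m = 5. Power is then about 65% to 66%.

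**4. Precision of the two missing contrasts**

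This assumes 40 analysable per cell and a common SD. The documents give no expected effect in controls or for the interaction, so the plan's own effect sizes serve as a range.

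- HC-OT vs HC-PBO: SE = √(2/40) = 0.224 SD. Detectable at 80% power: 2.80 × 0.224 = 0.63 SD. Power is 57% at 0.48 SD and 98% at 0.9 SD.
- Interaction: SE = √(4/40) = 0.316 SD. 95% CI half-width: 1.975 × 0.316 = 0.62 SD (156 df). Detectable at 80% power: 2.80 × 0.316 = 0.89 SD.
- Interaction power, Φ(δ/0.316 − 1.960): 33% at 0.48 SD, 66% at 0.75 SD, 81% at 0.9 SD.
- Sample needed for an interaction of 0.48 SD: 4 × (2.80/0.48)² ≈ 137 per cell.

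The plan's 0.9 is stated for CD-PBO vs HC-PBO. If oxytocin fully closed that gap in CD and did nothing in controls, the interaction would be 0.9 SD. If it also moved controls by half as much, the interaction would be 0.45 SD, with about 30% power.

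C3f excludes participants whose head motion exceeds 0.2 mm and gives no expected number. If 30 per cell remained (an illustration), the detectable interaction would be 2.80 × √(4/30) = 1.02 SD.

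**The case against.** The case against acting is substantial. None of the stated hypotheses involves HC-OT, and none concerns an interaction. The Significance sentence is background, speaks of exploring, and covers connectivity, anxiety and craving but not the response to faces. Tests 1A, 1B, 2A and 2B are valid as written. The interaction would be underpowered for all but large differences. A pooled four-group model gains little for the planned contrasts: moving from 78 to 156 error df takes the critical t only from 1.991 to 1.975.

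All of that stands, and it limits the point to an improvement in what the trial can say. It does not remove the gap. The oxytocin-treated controls are recruited, dosed and scanned, and the randomised comparison they make possible is not reported.

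A reader might go further and infer that these controls enter no test of oxytocin at all. The documents do not support that. The 1C model compares oxytocin with placebo in an unstated population, and its sample size fits only if controls are pooled in. The exploratory analysis of women also includes HC-OT, and the secondary whole-brain analysis does not exclude it. Nor can one say that the oxytocin aim goes unanalysed: 1B, 1C and 2B test oxytocin in CD participants.

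**Conclusion.** The point holds in limited form. For both imaging outcomes, no named test estimates oxytocin's effect in controls or the diagnosis-by-treatment interaction. The trial as planned therefore cannot say whether an oxytocin effect is particular to cocaine dependence. For connectivity this falls short of what the Significance section announces. For the amygdala response it is a missed use of the design, not a broken undertaking.

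For 1C the fault is an internal mismatch: a CD-only hypothesis, a sample size that includes controls, and a model with no stated population. If controls are pooled, equal oxytocin effects in the two groups are assumed without test. If they are not, power at d = 0.48 is 57% to 66%, not 80%.

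The precision figures (interaction half-width about 0.62 SD, detectable about 0.89 SD) assume 40 analysable per cell and a common SD, and worsen with motion exclusions. No planned hypothesis test is biased by any of this.

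**What to change.** - **Connectivity.** Fit one four-group second-level FLAME 1 model to the PPI images. Keep 1A and 1B as planned contrasts and add HC-OT vs HC-PBO and the interaction. Report these two with 95% CIs from PPI estimates extracted in OFC and ACC regions fixed in advance.
- **Left amygdala response.** Fit one 2x2 diagnosis-by-treatment linear model. Take 2A and 2B from it as planned contrasts and add the same two estimates.
- **Anxiety and craving.** Keep the repeated-measures mixed model with its baseline covariate, and add diagnosis and diagnosis-by-treatment terms. Define 1C as the CD-OT vs CD-PBO contrast, state that controls are in the model, and restate the power for that contrast.
- **HC-OT vs CD-OT.** The test may stay. Add a sentence that it will not be set against 1A as evidence of normalisation; the interaction estimate serves that purpose.
- **Status.** Label the added contrasts secondary or exploratory and present them as estimates. State in advance whether variances are common or group-specific.

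The cost is revised analysis text, a larger design matrix and an ROI extraction step. No new data are needed and every planned hypothesis is retained. The drawback is that the interaction will be imprecise, and a wide interval must not be reported as evidence of no difference.
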